## **7.4.2 Modifications of Study Therapy**

### **7.4.2.1 Dose Delays**

Each nivolumab and ipilimumab infusion may be delayed. A dose will be considered as actually delayed if the delay is exceeding 3 days (i.e., greater than or equal to 4 days from scheduled dosing date) for both nivolumab and ipilimumab. All study drugs must be delayed until treatment can resume. Reason for dose delay will be retrieved from CRF dosing pages.

The following parameters will be summarized by treatment group:

- Number of dose delays per subject, length of delay (4 - <8 days, 8 - <15 days, 15- <42 days, ≥42 days), and reason for delay.

### **7.4.2.2 Infusion Interruptions and Rate Changes**

Each nivolumab or ipilimumab infusion can be interrupted and/or the IV infusion rate can be reduced. This information will be retrieved from CRF dosing pages.

The following parameters will be summarized by treatment group:

- Number of subjects with at least one dose infusion interruption, the reason for interruption, and the number of infusion interruptions per subject.
- Number of subjects with at least one IV infusion rate reduction and the reason for reduction.

### **7.4.2.3 Dose Escalations**

Dose escalations are not permitted for either nivolumab or ipilimumab.

### **7.4.2.4 Dose Reductions**

Dose reductions are not permitted for either nivolumab or ipilimumab.

### **7.4.2.5 Dose Omissions**

Dose omissions are not permitted for either nivolumab or ipilimumab.

[REDACTED]

## **7.5 Efficacy**

The efficacy analyses will be performed on the SCLC expansion cohort (nivolumab and nivolumab 1 mg/kg + ipilimumab 3 mg/kg treatment groups).

### **7.5.1 Objective Response Rate**

#### **7.5.1.1 Analysis for Primary Objective of SCLC Expansion Cohort**

The primary objective for the SCLC expansion cohort is to compare the ORR as assessed by BICR for nivolumab monotherapy versus nivolumab combined with ipilimumab (nivolumab 1 mg/kg + ipilimumab 3 mg/kg). This primary objective will be assessed when all subjects have been assigned/treated for approximately 6 months.

The comparison of ORR as per BICR assessment will be conducted using a two-sided Cochran-Mantel-Haenszel (CMH) test stratified by the stratification factor as per IVRS [number of prior treatment lines (1 vs. 2 prior chemotherapy regimens)]. An associated odds ratio and 95% CI will also be computed. An estimate of the difference in ORRs and corresponding CI will be calculated using CMH methodology and stratified by the stratification factor per IVRS (number of prior treatment lines). The number and percentage of subjects in each category of best overall response as assessed by BICR per RECIST v1.1 criteria (complete response, partial response, stable disease, progressive disease, or unable to determine) will be presented by treatment group. An estimate of the response rate and an associated exact two-sided 95% CI using Clopper and Pearson method will be presented by treatment group.

Similar methods will be used to summarize ORR for each stratification factor [number of prior treatment lines (1 vs. 2 prior chemotherapy regimens)]. However, the p-value will not be provided for each stratification factor.

DOR as determined by the investigator or BICR will be summarized for subjects who achieve confirmed PR or CR using the Kaplan-Meier (KM) product-limit method. Median values of DOR, along with two-sided 95% CI using the log-log transformation will also be calculated by treatment group. In addition, the percentage of responders still in response at different time points (3, 6, 12, 18, and 24 months) will be presented based on the KM plot.

To summarize the magnitude of reduction in tumor burden, a waterfall plot of best percentage reduction from baseline in sum of diameters of target lesions will be generated.

#### **7.5.1.2 Sensitivity Analysis**

Sensitivity analyses of ORR will be performed using the following modification:

- Best unconfirmed overall response
- Best confirmed overall response where all response designations contribute to the BOR determination, regardless of start of subsequent therapy/crossover
- Best unconfirmed overall response where all response designations contribute to the BOR determination, regardless of start of subsequent therapy/crossover.

Sensitivity analyses of DOR will also be performed using the following modification:

- DOR accounting for assessment on/after subsequent therapy/crossover. DOR will be defined similarly to the primary analysis, but regardless of start of subsequent therapy/crossover.

## **7.5.2 Progression Free Survival**

### **7.5.2.1 Primary Analysis**

PFS is determined by the investigator or BICR. The PFS curves for each treatment group of the SCLC expansion cohort will be estimated using the KM product-limit method. Two-sided 95% CIs for median PFS will be computed using the log-log transformation.

PFS rates at 3, 6, 12, 18, and 24 months will be estimated using KM estimates on the PFS curve for each treatment arm of the SCLC expansion cohort. Minimum follow-up must be longer than the timepoint to generate the rate. The associated two-sided 95% CI will also be calculated. Additional survival analysis may be conducted for up to 5 years beyond analysis of the primary endpoint.

The source of progression (death vs. progression) will be summarized.

The status of subjects who are censored in the PFS KM analysis will be tabulated for each treatment arm in the expansion cohort using the following categories:

- On-study (on-treatment, in follow-up)
- Off-study (lost to follow-up, withdrawn consent, never treated)
- Received subsequent anti-cancer therapy

### **7.5.2.2 Sensitivity Analysis**

Sensitivity analyses of PFS will also be performed using the following modification:

- PFS accounting for assessment on/after subsequent therapy. PFS will be defined similarly to the primary analysis except that events (progression or death) and tumor assessments that occurred on or after subsequent anti-cancer therapy will be taken into account.

## **7.5.3 Overall Survival**

OS curves for each treatment arm in the SCLC expansion cohort will be estimated using the KM product limit method. Median OS and the corresponding two-sided 95% CIs using the log-log transformation will be computed. Survival rates at 3, 6, 12, 18, and 24 months will be estimated using KM estimates on the OS curve for each treatment arm in the expansion cohort. Minimum follow-up must be longer than the timepoint to generate the rate. Associated two-sided 95% CIs will be calculated. Additional survival analysis may be conducted for up to 5 years beyond analysis of the primary endpoint.

For crossover subjects, no data will be truncated.

### **7.5.3.1 Subject Follow-up**

The extent of follow-up defined as the time between assignment date and last known date alive (for subjects who are alive) or death date (for subjects who died) will be summarized descriptively (median, min, max) for all assigned subjects.

The currentness of follow-up, defined as the time between last OS contact (i.e., last known date alive or death date) and data cut-off date, will be summarized by treatment group for the SCLC expansion cohort. Subjects who died and subjects with a Last Known Date Alive on or after LPLV will have a value of '0' for currentness of follow-up. The currentness of follow-up will be categorized into the following categories: 0 days, >0 to <3 months, ≥3 to 6 months, ≥6-9 months, ≥9-12 months, ≥12-15 months, or ≥ 15 months.

### **7.5.3.2 Subsequent Therapy**

Subsequent therapy and response to subsequent therapy will be summarized and listed.

- Subsequent Therapy
  - Chemotherapy by drug name
  - Hormonal or biologic therapy by drug name
  - Immunotherapy (anti-PD1 agents, anti-PDL1 agents, anti-CTLA4 agents, and others) by drug name
  - BRAF inhibitor by drug name
  - MEK/NRAS inhibitor by drug name
  - Other investigational agent by drug name
  - Surgery
  - Radiography
  - Any combination of the above

A by-subject listing of follow-up therapy will be produced for subjects who had any subsequent therapy.

## **7.6 Safety**

For all safety related analyses, refer to the Core Safety SAP. As noted in [Section 7.1](#), safety will be summarized for all treated subjects in the SCLC pooled pre-expansion and expansion cohorts, by treatment group (Nivolumab and Nivolumab 1 mg/kg + Ipilimumab 3 mg/kg).

In addition, the following select safety summaries will be summarized for all subjects in the SCLC expansion cohort, by treatment group (Nivolumab and Nivolumab 1 mg/kg + Ipilimumab 3 mg/kg):

- Summary of Drug-Related Adverse Events by Worst CTC Grade (Any Grade, Grade 3-4, Grade 5)
- Summary of Drug-Related Serious Adverse Events by Worst CTC Grade (Any Grade, Grade 3-4, Grade 5)

- Summary of Drug-Related Adverse Events Leading to Discontinuation by Worst CTC Grade (Any Grade, Grade 3-4, Grade 5)
- Death Summary

For the analyses of crossover subjects during original assigned treatments, all the AE will be truncated at the first crossover dose date. All others will follow regular counting rules. For the analysis of crossover subjects during crossover period, all the AE will be counted at the first crossover dose date.

Treatment-related AEs leading to discontinuation will be tabulated using worst grade per NCI CTCAE v 4.0 criteria by system organ class and preferred term. All on-study AEs, Grade 3-4 AEs, treatment-related AEs, Grade 3-4 treatment-related AEs, SAEs, treatment-related SAEs, and AEs leading to discontinuation will be tabulated using worst grade per NCI CTCAE v 4.0 criteria by system organ class and preferred term. On-study lab parameters including hematology, chemistry, liver function, and renal function and Grade 3-4 Lab Abnormalities will be summarized using grade NCI CTCAE v 4.0 criteria.

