### **4.2 Secondary**

The secondary objective (to assess the safety and tolerability of nivolumab monotherapy or nivolumab combined with ipilimumab in subjects with advanced or metastatic tumors) will be primarily assessed by the rate of treatment-related AEs leading to drug discontinuations during the first 12 weeks of treatment. In addition, safety and tolerability will be analyzed through the incidence of adverse events, serious adverse events, and specific laboratory abnormalities (worst grade) in each cohort. Toxicities will be graded using the National Cancer Institute (NCI) Common Terminology Criteria for Adverse Events (CTCAE) version 4.0.

ORR will be further characterized by the duration of response (DOR) and the magnitude of reduction in tumor volume. DOR will be computed for subjects with a BOR of PR or CR and is defined as the time from first confirmed response (CR or PR) to the date of the first documented

tumor progression as determined using RECIST 1.1 criteria or death due to any cause, whichever occurs first. For subjects who neither progress nor die, the DOR will be censored on the date of their last evaluable tumor assessment. Subjects who start subsequent therapy without a prior reported progression will be censored at the last evaluable tumor assessments prior to initiation of the subsequent anticancer therapy. The magnitude of reduction in tumor volume is defined as the percent decrease in tumor volume from baseline to nadir, observed up until the time of the first documented tumor progression or death.

Progression free survival (PFS) is defined as the time from first dosing date to the date of the first documented progression, as determined by the investigator or BICR for selected tumor type (per RECIST 1.1), or death due to any cause, whichever occurs first. Subjects who die without a reported progression or start of any subsequent anti-cancer therapy will be considered to have progressed on the date of their death. Subjects who did not progress or die will be considered as not progressed and will be censored on the date of their last evaluable assessment or last evaluable assessment prior to crossover. Subjects who did not have any on study assessments and did not die will be censored on the first dosing date. Subjects who started any subsequent anti-cancer therapy without a prior reported progression will be censored at the last evaluable assessment prior to initiation of the subsequent anti-cancer therapy.

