## **7.6 Safety**

For all safety related analyses, refer to the Core Safety SAP. Safety will be summarized for: all treated subjects, by cohort; all dose escalation subjects, by tumor type; and all crossover subjects, by tumor type.

For the analyses of crossover subjects during original assigned treatments, all the AE will be truncated at the first crossover dose date. All others will follow regular counting rules. For the analysis of crossover subjects during crossover period, all the AE will be counted at the first crossover dose date.

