#### **6.1.2 Post Baseline Period**

On-treatment AEs will be defined as AEs with an onset date and time on or after the date and time of the first dose of study treatment (or with an onset date on or after the day of first dose of study treatment if time is not collected or is missing). An AE will be counted as on-treatment if the event occurred within 30/100 days of the last dose of study treatment.

On-treatment evaluations (laboratory tests, pulse oximetry, and vital signs) will be defined as evaluations taken after the day (and time, if collected and not missing) of first dose of study treatment. An evaluation will be counted as on-treatment if it occurred within 30/100 days of the last dose of study treatment.

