### **6.2 Treatment Regimens**

The treatment group “**as assigned**” will be retrieved from the IVRS system.

The treatment group “**as treated**” will be the same as the arm as assigned by IVRS. However, if a subject received the incorrect drug for **the entire period** of treatment the subject’s treatment group will be defined as the incorrect drug the subject actually received.

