## 7 STATISTICAL ANALYSES

### 7.1 General Methods

Unless otherwise noted, analyses outlined in [Sections 7.2](#) through [7.5](#) and [Section 7.9](#) will be performed using the SCLC expansion cohort treated with nivolumab monotherapy or with nivolumab in combination with ipilimumab (nivolumab 1 mg/kg + ipilimumab 3 mg/kg). Safety will be summarized for all treated subjects in the SCLC pooled pre-expansion and expansion cohorts, by treatment group (nivolumab and nivolumab 1 mg/kg + ipilimumab 3 mg/kg). All listings will be produced for the SCLC pooled pre-expansion and expansion cohorts.

The following subsections describe tabulations of discrete variables, by the frequency and proportion of subjects falling into each category, for the SCLC expansion cohort. Percentages given in these tables will be rounded and, therefore, may not always sum to 100%. Continuous variables will be summarized for the expansion cohort using the mean, standard deviation, median, minimum and maximum values.

Time to event distributions (i.e. overall survival, progression free survival, time to response, and duration of response) will be estimated using Kaplan Meier techniques. When appropriate, the

median along with 95% CI will be provided using Brookmeyer and Crowley methodology (using the log-log transformation for construction of confidence intervals). Rates at fixed timepoints (e.g. OS at 12 months) will be derived from the Kaplan Meier estimate along with their corresponding log-log transformed 95% confidence intervals. Confidence intervals for binomial proportions will be derived using the Clopper-Pearson method.

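### Among safety outcomes, only adverse events have a stated cut-off at crossover; laboratory, pulse-oximetry and vital-sign results have none

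*SAP*

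**What the plan says.** The rules are the same in both SAPs unless noted.

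- **Adverse events (7.6).** For crossover subjects analysed under their original treatment, "all the AE will be truncated at the first crossover dose date. All others will follow regular counting rules". Events in the crossover period are counted from that dose.
- **Laboratory tests, pulse oximetry, vital signs (6.1.2).** "On-treatment evaluations (laboratory tests, pulse oximetry, and vital signs) will be defined as evaluations taken after the day" (and time, where collected) of the first dose. The window closes as follows: "An evaluation will be counted as on-treatment if it occurred within 30/100 days of the last dose of study treatment". Crossover is not mentioned.
- **Treatment group (6.2).** The as-treated group "will be the same as the arm as assigned by IVRS", unless the wrong drug was given throughout. A subject who crosses over therefore stays in Arm N.
- **Use of laboratory data.** Under section 4.2 of SAP v2.0, "safety and tolerability will be analyzed through the incidence of adverse events, serious adverse events, and specific laboratory abnormalities (worst grade) in each cohort"; the expansion SAP has a parallel statement. Section 7.6 of the expansion SAP adds that "Grade 3-4 Lab Abnormalities will be summarized using grade NCI CTCAE v 4.0 criteria".
- **Safety set in the expansion SAP (7.1).** "Safety will be summarized for all treated subjects in the SCLC pooled pre-expansion and expansion cohorts, by treatment group". Section 2.1 of that SAP permitted crossover in the pre-expansion Arm N. It also reports that two expansion subjects crossed over although this was not allowed.
- **Deferral.** Section 7.6 of both SAPs refers safety analyses to the Core Safety SAP. In the expansion SAP, the subsections on hematology, serum chemistry, and vital signs and pulse oximetry contain only that reference.

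**The concern.** After crossover an Arm N subject receives ipilimumab as well as nivolumab. If the worst laboratory grade is taken over the whole section 6.1.2 window, it can come from the combination period and still be tabulated under nivolumab monotherapy. An adverse event from the same days would be excluded from that column. The adverse-event and laboratory tables for one arm would then cover different periods and different drugs.

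The error would run in one direction. Adding post-crossover results can raise the monotherapy laboratory rate but cannot lower it, and it leaves the combination group unchanged. If the combination has the higher rate, the apparent difference shrinks. The comparison of laboratory toxicity between the two regimens is what is at stake. The primary endpoint is not affected.

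**Working it through.** The plan states no figure that depends on this rule, so there is nothing to reproduce. The check compares the rules and then bounds the effect.

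**1. Which data have a crossover rule?**

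| Data | Rule at crossover | Where |
|---|---|---|
| Exposure | Cut | 7.4, both SAPs |
| PFS, crossover without progression | Censored at last evaluable assessment before crossover | 4.2 and its table, both SAPs |
| ORR, spider plot | Cut | 7.5.1.1, SAP v2.0 |
| Adverse events | Cut | 7.6, both SAPs |
| OS | Expressly not cut | 7.5.3, both SAPs |
| Laboratory, pulse oximetry, vital signs | Nothing stated | 6.1.2 and 7.6 |

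For the other data types the plan says whether to cut. For these evaluations it says neither.

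**2. Does the answer depend on what the last dose of study treatment means?** Section 6.1.2 does not say whether crossover dosing counts.

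- If it counts, the window covers the whole combination period plus 30/100 days.
- If it does not, the window starts at the last monotherapy dose. Assume the first crossover dose comes 14 to 28 days later (the documents give no interval). The 100-day window then still holds 100 − 28 = 72 to 100 − 14 = 86 days of combination treatment. The 30-day window holds 30 − 28 = 2 to 30 − 14 = 16 days. With dosing every 3 weeks, the fourth combination dose falls 3 × 21 = 63 days after the first, inside the 72 to 86 days.

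The gap therefore exists under either reading. The adverse-event window in 6.1.2 has the same 30/100-day limit, and section 7.6 still adds a crossover cut-off for adverse events.

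**3. How large could it be in the expansion SAP's pooled tables?** Let c be the number of crossover subjects, q the share whose qualifying laboratory abnormality appears only after crossover, and N the number of nivolumab subjects.

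Points added to the monotherapy rate = 100 × c × q / N

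- N = 150 (planned expansion, section 5) + 100 (planned pre-expansion maximum, section 2.1) = 250.
- Known crossovers only: c = 2 (section 2.1), with q = 1 as the extreme. 100 × 2 × 1 / 250 = 0.8 points.
- Illustration with assumed c and q: c = 10, q = 0.1 gives 100 × 10 × 0.1 / 250 = 0.4 points; c = 30, q = 0.5 gives 100 × 30 × 0.5 / 250 = 6.0 points. With two crossovers from the expansion cohort, c = 30 means 28 of at most 100 pre-expansion subjects.

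The combination rate is untouched, so if it is the higher one, the difference narrows by the same number of points.

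**The case against.** **The Core Safety SAP may already hold the rule.** This is the strongest point against the concern, and it cannot be checked. For SAP v2.0, the text at hand also lacks the subsections on serum chemistry and on vital signs that its contents page lists. The consequence must therefore be stated conditionally. The deferral does not settle the matter, though. Adverse events are referred to the same document, yet their crossover rule is written out here. The laboratory window is defined here too, and section 2.1 of the expansion SAP says that the handling of crossover subjects is described in what follows.

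**Readings that go too far.** A reader might take the sentence about all others following regular counting rules to send laboratory data to the ordinary window. The same sentence follows the exposure rule in 7.4, where it most naturally means all other subjects, so it does not show this. A reader might also take the window to run from the last dose of any treatment, crossover included. Section 6.1.2 does not say so, and 7.6 separates the original and crossover periods. Nor do the documents show that monotherapy rates will in fact be biased. They show only that the stated rules permit it.

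**Size and importance.** Safety is assessed first by treatment-related adverse events leading to discontinuation in the first 12 weeks, for which the crossover cut-off is stated. Laboratory results are an additional, descriptive summary. The expansion-only safety summaries listed in 7.6 contain no laboratory table, so the two expansion crossovers matter only through the pooled set. Subjects with nivolumab-related events leading to permanent discontinuation could not cross over. Crossover went to Dose Level 2b once that level was active, whereas the expansion comparator is Dose Level 2, so one assumed combination rate cannot serve for both. All of this stands. It limits what can be claimed about size but does not remove the gap.

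**Conclusion.** The point holds in a conditional form. Among safety outcomes, both SAPs state a crossover cut-off only for adverse events. Laboratory, pulse-oximetry and vital-sign results have a window with no crossover limit, and the subject remains in the assigned arm. Unless the Core Safety SAP prevents it, results obtained on the combination can be counted under nivolumab monotherapy while adverse events from the same period are removed.

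The only bound that rests on a documented crossover count is at most 0.8 points in the pooled SCLC tables. It comes from the two known expansion crossovers and assumes the planned 250 nivolumab subjects; fewer subjects would raise it somewhat. The range of 0.4 to 6.0 points rests on assumed crossover numbers and laboratory rates and is an illustration, not an estimate. A reader might infer a large bias or a seriously blurred safety comparison. The documents give neither the crossover number for the pooled set nor any laboratory rates, so they do not support that. For the other tumor types in SAP v2.0 the size is unknown for the same reason.

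**What to change.** In section 7.6 of both SAPs, state that for crossover subjects the laboratory, pulse-oximetry and vital-sign evaluations in the original-treatment analysis are truncated at the date of the first crossover dose, as adverse events are, and that later evaluations are reported in the crossover-period summary. In section 6.1.2, add that the original-treatment window for these subjects ends at that date if it comes before the 30/100-day limit. If the Core Safety SAP already contains such a rule, citing it in both places is enough.

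The cost is a few sentences and one date condition in the laboratory and vital-sign programs, with no new data. A few evaluations move from the Arm N tables to the crossover tables. This is a counting rule for analysis only and changes no clinical management.
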